5. STUDY TREATMENT

5.1. Overall Study Design Investigational Study Drug

Detailed information about MS-553 is available in the IB and the Pharmacy Manual.

5.1.1. MS-553 Treatment Description

MS-553 drug product is supplied as an immediate release, round, white film-coated tablet provided in three strengths: 25 mg, 50 mg and 100 mg. The precise composition of the drug product and purpose of all ingredients are provided in the IB.

5.1.1.1. Storage and Handling

MS-553 drug product drug product is packaged in white, opaque, high-density polyethylene bottles with white, opaque, polypropylene, child resistant caps. Counts of 30 tablets each for 25 mg, 50 mg and 100 mg strength tablets are provided. Each bottle will be labeled with its contents, product lot number, required storage conditions, Sponsor's address, and any specific cautionary statement such as "New Drug – Limited by Federal Law to Investigational Use." Bottles are to be stored at room temperature (15-30°C). Until dispensed to the patients, MS-553 drug product bottles should be stored in a securely locked area accessible only to authorized site personnel. The MS-553 drug product should not be repackaged into alternative containers other than the bottles in which it was supplied. Refer to the Pharmacy Manual for more specific storage and handling information.

5.1.1.2. Study Drug Disposal

Used (empty) bottles and opened bottles with unused study drug supplies will be destroyed on-site by the Investigational Pharmacy Service according to the site SOP after completion of study drug accountability by the study monitor. Study drug destruction will be documented in the study's pharmacy binder. Unopened bottles will be returned to MingSight Pharmaceuticals Inc. or destroyed per the site SOP.

5.1.2. Combination Treatment Description

Combination treatment with either acalabrutinib (B Series Cohorts) or venetoclax and rituximab (C Series Cohorts) will be according to standard of care and as described in Section 5.2.3.2 and 5.2.3.3, respectively. The combination drugs should be stored, handled and disposed of according to the Complete Prescribing Information and site standard procedures for these drugs.

5.2. Treatment Plan

5.2.1. Premedication

Appropriate anti-emetic drugs per institutional standard should be administered upon initiation of MS-553.

5.2.2. Administration Instructions

MS-553 should be taken orally with food at approximately the same time each day. Patients should be instructed not to bite, chew or crush the tablet. If the patient is unable to take the entire tablet, contact the medical monitor for further instructions. Refer to the Pharmacy Manual for more specific dose administration details.

5.2.3. Dosing Instructions and Schedule

5.2.3.1. MS-553 Dosing – All Cohorts

MS-553 should be taken orally twice daily, every 12 hours \pm 2 hours. At C1D1, C1D8, and C2D1, the morning dose will be administered by clinic staff. All other doses will be administered by the patient. MS-553 should be taken at approximately the same time each day. Small variations in the twelve-hour schedule are understandable, but patients should be advised to adhere to the prescribed schedule as closely as possible. Adherence to the dosing schedule will be documented in the patient chart and EDC /electronic CRF at each scheduled visit. Patients will record all at-home dosing in a patient diary. Refer to the Pharmacy Manual for more specific dose administration details.

Administration Instructions: Dosing Interruptions, Missed Doses, and Vomited Doses

If a dose is late but within 4 hours of its scheduled administration time it should be taken; if more than 4 hours have passed, the dose should be omitted and the patient should continue treatment with the next scheduled dose with no alteration of timing for the subsequent dose. The missed dose should be documented in the patient's diary, chart and the EDC / electronic CRF.

If vomiting occurs while taking MS-553, no re-dosing is allowed before the next scheduled dose. Treating physicians are encouraged to use prophylactic antiemetics per standard of care at their institution.

Patients should be instructed that if they miss two or more doses consecutively that they must contact the investigator or other study site personnel.

5.2.3.2. Acalabrutinib Dosing – B Cohorts

For patients who are enrolled into any of the B series cohorts, acalabrutinib will be administered according to the Full Prescribing Information in combination with MS-553. As both acalabrutinib and MS-553 are substrates of P-glycoprotein (P-gp), it is recommended that acalabrutinib be taken 90 minutes (but at least 1 hour) prior to the time when MS-553 is taken to avoid potential drug-drug interaction.

5.2.3.3. Venetoclax and Rituximab Dosing – C Cohorts

For patients are enrolled into any of the C series cohorts, venetoclax will be initiated after eight weeks of treatment with MS-553 and rituximab. Rituximab will be administered according to the Full Prescribing Information except the necessary changes to allow for the dosing sequence of the triple drug combination regimen. In order to reduce the risk of TLS, venetoclax will not be administered until Cycle 3. Beginning in Cycle 3, venetoclax will be started and dose escalated in accordance with the Prescribing Information from 20 mg to 400 mg over five (5) weeks and administered in combination with rituximab and MS-533. Venetoclax should be taken with food \geq 6 hr after the morning dose of MS-553. Venetoclax shall be administered in accordance with the Full Prescribing Information.

For patients who have achieved complete responses with the treatment of the triplet regimen of MS-553, venetoclax, and rituximab, assessments of uMRD in a central lab will be performed in a fashion consistent with IWCLL 2018 guideline. If uMRD in both peripheral blood and bone marrow is confirmed in a central lab, MS-553 may be discontinued at the discretion of the investigators after completion of venetoclax administration as defined in package label.

5.2.4. Concomitant and Supportive Therapy

5.2.4.1. MS-553

Treating physicians are encouraged to use prophylactic antiemetics per standard of care at their institution.

Steroids in doses of up to 20 mg prednisone (or equivalent) daily are allowed for symptomatic relief of lymphadenopathy and B symptoms if needed, with preference for their administration to be delayed until after completion of Cycle 1. If steroids are needed to control lymphadenopathy-related issues, please discuss with the medical monitor/Sponsor. After completion of Cycle 1, higher dose steroids may only be used for therapeutic treatment of (1) GVHD or (2) autoimmune cytopenia after discussion with the medical monitor and/or Sponsor. Treatment with short courses of steroids is permitted for intercurrent illness as per standard of care practice.

No other direct anti-leukemia therapy is permitted.

Supportive care with blood products (prophylactic or therapeutic) and hematopoietic growth factors may be used in accordance with institutional standards. Use of myeloid or erythroid growth factor during DLT period should be discussed with the medical monitor and the study Sponsor.

5.2.4.2. Acalabrutinib

Treating physicians are encouraged to use concomitant and supportive therapy for acalabrutinib per standard of care at their institution.

5.2.4.3. Venetoclax

Prior to initiation of venetoclax, MS-553 and rituximab combination shall be given for two cycles to allow for debulking of tumor mass with the intent of avoiding tumor lysis syndrome (TLS). Venetoclax shall start on Cycle 3. Treating physicians should assess patient-specific factors for level of risk of TLS and provide prophylactic hydration and anti-hyperuricemics to patients prior to the first dose of venetoclax to reduce risk of TLS according to standard site procedures. After two cycles treatment of MS-553 and rituximab, restaging prior to Cycle 3 at

investigator discretion is allowed for patients who were initially high risk for TLS, to allow outpatient treatment if they now are low or medium risk.

Table 6:Recommended TLS Prophylaxis Based on Tumor Burden in Patients with
CLL/SLL

Tumor Burden	Prophylaxis		Blood Chemistry Monitoring ^{cde}
	Hydration ^a	Anti- hyperuricemics	Frequency of Assessments
All LN < 5cm AND ALC < 25 x 10 ⁹ /L	Oral (1.5-2 L)	Allopurinol ^b	 First dose of 20 mg and 50 mg: Pre-dose, 6 to 8 hours, 24 hours For subsequent ramp-up doses: Pre-dose
Any LN \geq 5cm to < 10cm OR ALC \geq 25 x 10 ⁹ /L	Oral (1.5-2 L) and consider additional intravenous	Allopurinol	 First dose of 20 mg and 50 mg: Pre-dose, 6 to 8 hours, 24 hours For subsequent ramp-up doses: Pre-dose For first dose of 20mg and 50mg: Consider hospitalization for patients with CrCl < 80 mL/min
$\begin{tabular}{l} LN \geqslant 10 cm \\ OR \\ ALC \geqslant 25 \ x \\ 10^9/L \\ AND \ any \ LN \geqslant 5 \\ cm \end{tabular}$	Oral (1.5-2 L) and intravenous (150-200 mL/hr as tolerated)	Allopurinol; consider rasburicase if baseline uric acid is elevated	 In hospital first dose of 20 mg and 50 mg: Pre-dose, 4, 8, 12, 24 hours For subsequent ramp-up doses, outpatient: Pre-dose, 6 to 8 hours, 24 hours

^{a.} Administer intravenous hydration for any patient who cannot tolerate oral hydration

^{b.} Start allopurinol or xanthine oxidase inhibitor 2 to 3 days prior to initiation of venetoclax

^c Evaluate blood chemistries (potassium, uric acid, phosphorus, calcium, and creatinine); review in real time.

^{d.} For patients at risk of TLS, monitor blood chemistries at 6 to 8 hours and at 24 hours at each subsequent ramp-up dose or according to institutional standard.

^{e.} A window of one hour is permitted for the post-dose labs that are due <24 hours and a two-hour window is permitted for the 24-hour post dose labs.

To reduce risks associated with neutropenia, granulocyte-colony stimulating factor (G-CSF) may be administered, if clinically indicated.

5.2.4.4. Anti-CD20 mAb

Consistent with the Prescribing Information of venetoclax, the anti-CD20 mAb used in the combination shall be rituximab for the relapsed/refractory CLL/SLL patients. Premedicate with acetaminophen and an antihistamine before each rituximab infusion according to institutional standard of care. Depending on the severity of any infusion-related reaction and the required

interventions, temporarily or permanently discontinue rituximab. Resume infusion according to institutional standard of care after symptoms have resolved.

Provide prophylaxis treatment for Pneumocystis jirovecii pneumonia (PCP) and herpes virus infections for patients with CLL during treatment and for up to 12 months following treatment as appropriate.

5.2.5. Excluded Medications

Co-administration of strong (\geq 5-fold) inhibitors or inducers and sensitive substrates of CYP3A4/5 is prohibited and should be discontinued at least 48 hours prior to initiation of study drug. Medications with QT prolongation risk as listed in their package inserts or belong to drugs with known risk of Torsades de Pointers on crediblemeds.org should be avoided whenever possible. Refer to Appendix 3 for examples of these medications. When substitution of another medication is not feasible, discussion with the medical monitor and Sponsor will be needed. For example, the metabolism of the drug in question may be more affected by other P450 enzymes and not CYP3A4 or CYP3A5, in which case use of that drug may be approvable for use in the study. If in doubt, please discuss with the medical monitor.

Systemic steroids (not inhalation or topical) in amounts of 20 mg or higher of prednisone or equivalent per day may be permitted under certain circumstances (e.g., as pre- and post-medication for reactions to contrast agents; treatment of pre-existing disease-related autoimmune cytopenias and hemolysis; those treated for GVHD; those with an acute need for a non-disease related condition (e.g., additional steroid requirement for adrenal insufficiency or other acute condition where a short course [up to 14 days] may be required). In such circumstances of non-disease-related conditions, please discuss with the medical monitor/Sponsor regarding continuation of dosing of study drug during this period of increased steroid administration. Patients may not receive any other anticancer therapies for the current malignancy while on study prior to disease progression.

Supportive care with blood products (prophylactic or therapeutic) and hematopoietic growth factors may be used in accordance with institutional standards, however the use of myeloid or erythroid growth factor during the DLT evaluation period should be discussed with the medical monitor and the study Sponsor.

Cohorts using combination with acalabrutinib (B Cohorts)

Concomitant strong CYP3A inhibitors, CYP3A inducers or proton pump inhibitors are prohibited. Dose modifications should be used according to the Prescribing Information and institutional standard of care for concomitant moderate CYP3A inhibitors. Treating physicians should avoid co-administration with proton pump inhibitors. If the patient is taking antacids, patients should be advised to separate dosing by at least 2 hours of taking antacids. If the patient is taking an H2 receptor antagonist, patients should be advised to take acalabrutinib 2 hours prior to the H2 receptor antagonist.

Cohorts using combination with venetoclax (C Cohorts)

Strong and moderate CYP3A inhibitors/inducers or strong P-gp inhibitors are prohibited. As MS-553 may be a P-gp substrate, patients must avoid taking venetoclax together with MS-553 at the same time. A six-hour interval between MS-553 and venetoclax is advised.

5.3. Withdrawal Criteria

Patients will be advised that they are free to withdraw from the study at any time for any reason. A patient may be withdrawn from the study for any of the following reasons:

- Patient voluntarily discontinues study participation (consent withdrawal);
- The need to take medication which may interfere with study measurements;
- Adverse events;
- Disease progression; Exceptions may be allowed if continuing study drug beyond disease progression is needed and prior consent of the medical monitor is obtained;
- Major violation or deviation of study protocol procedures;
- Non-compliance of patient with protocol;
- Patient is unable to comply with study procedures;
- Withdrawal from the study is, in the Investigator's judgment, in the patient's best interest;
- Patient is lost to follow-up;
- Study termination by the Sponsor.

The reasons for withdrawal will be recorded on the CRF and included in the final report along with any adverse events and any necessary medical treatment.

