3.2. Treatment Duration

Patients will be treated in 28-day cycles. Patients on this study may continue receiving study drug provided they continue to tolerate the drug, have no evidence of progression, do not meet any of the criteria for discontinuation, and the patient's participation in the study has not ended. The anticipated median treatment duration is unknown. Patients who have discontinued treatment for progressive disease and/or who have started another anticancer therapy or an investigational

product, will be followed for survival every 24 weeks (± 7 days) for up to 3 years (follow up can include clinic visit, chart review or telephone contact). Patients who discontinue treatment for reasons other than progressive disease, use of other anticancer therapy or an investigational product, death, or withdrawal of consent will have response assessments every 12 weeks (± 7 days) until progressive disease occurs. Thereafter they will be followed for survival every 24 weeks (± 7 days) for up to 3 years. All patients will discontinue survival follow-up upon completion of 3 years of survival follow-up, withdrawal of consent, death, or study closure, whichever is the earliest. The Sponsor reserves the right to discontinue the study for clinical or administrative reasons at any time.

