3.7. Response Assessment

Response data will be collected at screening and on day 1 of every cycle beginning with the first treatment visit and ending at the end of treatment visit, which should occur 30 (+ 7 days) after the last dose of study drug, if the condition of the patient permits, or up to the start of other anti-cancer therapy or investigational drug product(s), whichever is sooner. Patients who discontinue treatment for reasons other than progressive disease, use of other anticancer therapy or an investigational drug product, death, or withdrawal of consent will undergo response assessments every 12 weeks (± 7 days) until progressive disease occurs.

Response data consists of a combination of interviews, physical exams, labs, and scans. Not all labs and scans will be obtained at each time point. See Section 6.2 and Appendix 1 for complete details.

4. **PATIENT POPULATION**

CLL is most commonly a disease of the elderly, with a median age at diagnosis of 71, but disease has been witnessed in adults of all ages. This study is targeted at CLL adults of any age who meet the inclusion criteria for the cohort to which the patient is enrolled.

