5.4. Discontinued Patients

Notification of early patient discontinuation from the study and the reason for discontinuation will be made to the Sponsor (or designee) and will be clearly documented on the appropriate electronic CRF. If a patient is discontinued from the study early, all End of Treatment visit evaluations should be performed at the time of discontinuation, if possible.

Patients who are withdrawn or discontinue early may be replaced at the discretion of the Sponsor.

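### Section 5.3 allows withdrawal from the study for adverse events or progression, while Section 3.2 requires such patients to be followed; acting on 5.3 can censor OS, and after an adverse-event stop PFS and DoR too, at a point related to prognosis

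*Combined protocol and SAP*

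**What the plan says.** **Leaving the study.** Section 5.3 opens its list with "A patient may be withdrawn from the study for any of the following reasons". The reasons include "Adverse events" and "Disease progression; Exceptions may be allowed if continuing study drug beyond disease progression is needed and prior consent of the medical monitor is obtained", together with interfering medication, major protocol violation, non-compliance, inability to comply and investigator judgement. The same list holds consent withdrawal, loss to follow-up and study termination. Nothing separates the two kinds.

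Section 5.4 continues: "If a patient is discontinued from the study early, all End of Treatment visit evaluations should be performed at the time of discontinuation, if possible". It mentions no later contact and adds that "Patients who are withdrawn or discontinue early may be replaced at the discretion of the Sponsor".

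**Follow-up after stopping treatment.** Under Section 3.2, a patient who stops for progression or starts another therapy is contacted for survival every 24 weeks for up to 3 years. A patient who stops for another reason, which includes an adverse event, is assessed for response every 12 weeks until progression and then followed for survival. Section 3.2 closes with "All patients will discontinue survival follow-up upon completion of 3 years of survival follow-up, withdrawal of consent, death, or study closure", whichever comes first. The synopsis and footnote b of Appendices 1A to 1C say the same. Section 3.7 repeats the response part only: such patients "will undergo response assessments every 12 weeks (± 7 days) until progressive disease occurs".

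**Censoring.** Section 6.2.2 censors DoR, PFS and OS at last known status for patients without the event.

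**The concern.** Adverse events and progression are grounds for leaving the study in 5.3, but they are not among the events that end survival follow-up in 3.2. Two sites with the same kind of patient could each follow a section of the protocol and handle the patient differently: one closes the patient out after the End of Treatment visit, the other continues the 12-weekly or 24-weekly contact.

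The first patient is then censored at last known status. Kaplan-Meier methods assume that censoring is unrelated to prognosis, and close-out at progression or toxicity need not be. The study plans up to about 15 sites, and its expansion groups are small (about 10 patients in B3, 20 in B2 and in C2), so a few patients handled differently can move an estimate. Follow-up missed after close-out may not be recoverable.

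**Working it through.** The plan states no figure on this point to reproduce. The check sets the sections side by side and then gauges the size on assumed inputs.

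**1. Which endpoint is exposed**

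| Reason for close-out under 5.3 | Follow-up required by 3.2 | Endpoint that can be affected |
|---|---|---|
| Progression | Survival, every 24 weeks | OS only; progression is already a PFS and DoR event (Section 2.5) |
| Adverse event before progression | Response every 12 weeks until progression, then survival | PFS, DoR in responders, OS |
| Consent withdrawal, study termination | None; both sections agree | None from this conflict |

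**2. Whether another rule settles it.** Section 6.2.2 refers to Section 8 for further censoring details. Section 8.8, as published, covers ORR only, so nothing shown there treats a site's close-out differently from other censoring.

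**3. Size for OS at 24 months (all rates assumed).** Let *a* be the progression hazard, *b* the death hazard before progression, *d* the death hazard after it, and *s* the share of progressors closed out at progression.

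- Alive without progression: A(u) = exp(−(a+b)u).
- Alive after progression: B(u) = a/(a+b−d) × [exp(−du) − exp(−(a+b)u)].
- True OS = A(24) + B(24).
- Kaplan-Meier limit with close-out = exp(−∫h du) over 0 to 24, where h = [bA + d(1−s)B] / [A + (1−s)B].

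Example with a = 0.05, b = 0.005, d = 0.02 per month: A = exp(−1.32) = 0.267; B = (0.05/0.035) × (0.619 − 0.267) = 0.502; true OS = 0.769. With s = 1 the estimate is exp(−0.005 × 24) = 0.887.

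| Assumed inputs | True OS | s = 25% | s = 50% | s = 100% |
|---|---|---|---|---|
| a 0.05, b 0.005, d 0.02 | 76.9% | +1.6 | +3.8 | +11.7 |
| a 0.05, b 0.005, d 0.04 | 65.3% | +3.2 | +7.5 | +23.4 |
| a = ln2/12, b = a/10, d = ln2/24 | 68.8% | +2.3 | +5.4 | +18.2 |
| a = ln2/12, b = a/10, d = ln2/12 | 54.1% | +4.1 | +9.8 | +32.9 |

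Entries under *s* are percentage points of overstatement.

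**4. Size for PFS at 12 months (all rates assumed).** Take a median PFS of 12 months on drug, so L = ln2/12 = 0.0578. Let *q* be the share who would stop for an adverse event by 12 months, so w = −ln(1−q)/12, and let the hazard after the stop be *m* × L.

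- E = exp(−12(L+w)).
- True PFS = E + w/(L+w−mL) × [exp(−12mL) − E].
- Estimate with close-out at the stop = exp(−12L) = 0.500.

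Example with q = 20%, m = 2: w = 0.0186; E = 0.5 × 0.8 = 0.400; true PFS = 0.400 + (0.0186/−0.0392) × (0.250 − 0.400) = 0.471; overstatement 2.9 points.

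| m | q = 10% | q = 20% | q = 30% |
|---|---|---|---|
| 0.5 | −1.0 | −2.0 | −3.1 |
| 1 | 0 | 0 | 0 |
| 1.5 | +0.8 | +1.6 | +2.5 |
| 2 | +1.4 | +2.9 | +4.4 |
| 3 | +2.3 | +4.7 | +7.2 |

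For PFS, the sign and the size both depend on what happens to the hazard after the stop, and the documents give no figure for it.

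**The case against.** The best defence is that 5.3 is permissive and cancels nothing, while mandatory follow-up text for the same patients stands in 3.2, the synopsis and three appendix footnotes. The context of 5.3 and 5.4 also suggests that stopping treatment was meant: the progression exception concerns continuing the drug, 5.4 calls for End of Treatment evaluations, and each Appendix 1 calendar places a follow-up column after that visit. Sections 6.1.7 and 7.7.1 further require follow-up of patients who stop for an adverse event until it resolves or stabilises.

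Most of this stands. It makes a drafting conflation the likely explanation, and divergent site practice is a possibility, not something the documents show. It does not remove the conflict. The text says study where it probably means treatment, although Section 6.1.7 uses the narrower term elsewhere, and the adverse-event follow-up in 6.1.7 and 7.7.1 collects neither progression nor survival.

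A reader might infer three stronger things that the documents do not support:

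- That 5.3 ends follow-up for these patients. It allows withdrawal and is silent on follow-up.
- That PFS, DoR and OS are all lost whenever 5.3 is used. Close-out at progression touches OS only.
- That the error always flatters MS-553. For OS after progression a worse prognosis is a safe premise. For adverse-event stops it is an assumption, and with an unchanged hazard the bias is zero. Section 6.2.2 also allows PFS and DoR to be censored at subsequent treatment, so some of that follow-up might be censored even when visits take place.

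**Conclusion.** The conflict between 5.3/5.4 and 3.2 is real and should be reconciled. A stated permission to withdraw contradicts a stated follow-up rule, and the censoring rule turns any close-out into censoring that may be informative.

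The size cannot be computed from the documents. In the assumed scenarios, 24-month OS is overstated by 1.6 to 4.1 points with 25% of progressors closed out and by 3.8 to 9.8 with half. The range of 11.7 to 32.9 points needs every progressor closed out at every site and should not be read as a forecast. PFS bias is zero with an unchanged hazard after the stop and reaches 7.2 points only in the most extreme scenario tried (30% stopping, tripled hazard).

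These are secondary, descriptive endpoints, and Section 8.4 states that no formal hypothesis is tested. The consequence is possible bias in reported estimates, with no effect on power or error control.

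**What to change.** Reconcile 5.3 and 5.4 with 3.2 in three statements:

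1. Stopping study treatment is distinct from leaving the study.
2. A patient who stops treatment for a 5.3 reason other than consent withdrawal, loss to follow-up or study termination enters the 3.2/3.7 follow-up after the End of Treatment visit.
3. Follow-up ends only at the events that 3.2 lists, including completion of 3 years, or at loss to follow-up.

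Record treatment stop and study exit as separate items, each with date and reason, if the eCRF does not already do so; it is not among the documents.

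Sections 5.3 and 3.6 also give different lists of reasons for ending treatment. The sponsor should reconcile them; this review does not propose which grounds should apply.

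The cost is a wording amendment and possibly one eCRF change. No visit is added, because 3.2 and Appendix 1 already schedule the follow-up. The change is worth most while patients can still be contacted.
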